Data Collection Instrument	Status
Volunteer Demographics	Incomplete
Screening Data	Incomplete (no data saved)
Randomization Form	Incomplete (no data saved)
Baseline Data	Incomplete (no data saved)
12-Week Follow-up Data	Incomplete (no data saved)
24-Week Follow-up Data	Incomplete (no data saved)

Legend for status icons:

- Incomplete (Red)
- Incomplete (no data saved) (Grey)
- Unverified (Yellow)
- Complete (Green)

- Any of the 3 RAs will call the volunteer, if the corresponding **Screening Data instrument** is not completed (i.e., not green), using the phone number in the **MCI Participant Demographics instrument**.
 - If the **volunteer** have approximately 30 minutes at the time of zoom call,
 - Each volunteer is asked for their demographic information, including gender, age, etc., which will be entered in the **MCI Participant Demographics instrument**.
 - If a caregiver participates in the study, each caregiver is asked for their demographic information, including gender, age, etc., which will be entered in the **Caregiver Demographics instrument**.

[figure not shown]
- Each volunteer is asked **inclusion and exclusion questions** (See [Appendix 2](#) for the inclusion & exclusion questions), answers of which will be entered in **the Screening Data instrument**.
- The volunteer's caregiver will be asked **inclusion and exclusion questions, the answers of which will be entered in the Screening Data instrument**. The fields are popped up when selecting 'Yes' to the questions 'Is a caregiver available to participate in this study'?
 - The volunteer, scoring MoCA 17 <= (score) < 26, will be included in our study.
- If both the volunteer and the active caregiver are eligible to join the study,
 - The RA will ask the **volunteer** and his/her active **caregiver** for their contact information, including their name, email address, and phone number if not collected yet, which will be entered in **the MCI Participant/Caregiver Demographics instrument**.
 - The RA will inform the volunteer and the active caregiver that the informed consent documents will be sent to them via email, and ask them to read, sign, and return the signed informed consent form.
 - The RA will change **the Form Status (Complete) field of the Screening Data** to Complete (i.e., green color). Green color indicates that the volunteer and the active caregiver are eligible for our study.
- If either the volunteer or the active caregiver or none of them is/are eligible to join the study,

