 - **(Videoconference version)** Montreal Cognitive Assessment (**MoCA**): Chapman, J. E., Cadilhac, D. A., Gardner, B., Ponsford, J., Bhalla, R., & Stolwyk, R. J. (2019). Comparing face-to-face and videoconference completion of the Montreal Cognitive Assessment (MoCA) in community-based survivors of stroke. *Journal of telemedicine and telecare*, 1357633X19890788.
 - **(Videoconference version)** Mini-Mental State Examination (**MMSE**): Timpano, F., Pirrotta, F., Bonanno, L., Marino, S., Marra, A., Bramanti, P., & Lanzafame, P. (2013). Videoconference-based mini mental state examination: a validation study. *Telemedicine and e-Health*, 19(12), 931-937.
 - **(Original)** Digit Forward Span (**DFS** from WAIS-IV): Powell, D. H., & Hiatt, M. D. (1996). Auditory and visual recall of forward and backward digit spans. *Perceptual and Motor Skills*, 82(3_suppl), 1099-1103.
 - **(Original)** Digit Backward Span (**DBS** from WAIS-IV): Powell, D. H., & Hiatt, M. D. (1996). Auditory and visual recall of forward and backward digit spans. *Perceptual and Motor Skills*, 82(3_suppl), 1099-1103.
 - **(Original)** Geriatric Depression Scale (**GDS**)
 - **(Original)** Short Form 36 (**SF-36**)
 - **(Original)** Alzheimer’s Disease Cooperative Study/ADL scale adapted for MCI participants (**ADCS/MCI/ADL24**)
- When the Rutgers RA completes the assessments, he/she will message the UMass RA in the smart phone texting group.
- The UMass RA will unmute.

- The Rutgers RA will leave.
- The UMass RA enters the address in **the Address to ship the tablet computer field of the MCI Participant Demographics instrument.**
- The UMass RA will inform the participant about the assignment result and explain the schedule.
 - Group A

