- Did you find the instructions in the games easy to understand?
- Was it easy to navigate the menu?
- How do you think we can improve the menu?

- Any comments?
 - Is there anything else you want to share with us?

- List of potential questions for the caregiver.

- How often did you have to remind the participant? Was this a burden for you?
- How much assistance did you have to provide help to participants?
- Did the participant avoid, complain, or otherwise protest when it was time to play Neuro-World?
- What advice do you have for us as we move forward with this research on Neuro-World training for persons diagnosed with MCI?

12. Assessment after 24 weeks (Only Rutgers RA can perform assessment; UMass RAs will organize the overall meeting)

- After 24 weeks, all participants will be assessed with the following tests **online (via zoom)**.

Detailed steps will be the same as the baseline assessment.

RAs will generate a new form for recording 24 weeks follow-up assessment from the corresponding **Assessment Form instrument**.

[figure not shown]
Towards the Development of a Mobile-Health Technology Based on Serious Game-based Interventions in Adults with MCI outside the clinic

Purpose

The purpose of this study is to learn: 1) if Neuro-World (mobile cognitive training games) can improve the cognitive function of adults with mild cognitive impairment (MCI), 2) if we can understand the cognitive function of adults with MCI based on their performance in Neuro-World, and 3) if we can learn practical challenges that adults with MCI face while playing Neuro-World.

Neuro-World

A tablet computer with pre-installed Neuro-world cognitive training games will be provided during the study.

Eligibility

Adults with MCI are eligible for the study if you 1) have mild cognitive impairment (we will assess your impairment level for you), 2) are 55 years old or older, 3) can use a tablet independently, and 4) have access to a computer for online video communication (e.g., Zoom).

Adults with MCI CANNOT participate in this study if you have 1) another neurologic or psychiatric disorder, 2) history of traumatic brain injury, 3) uncorrected hearing or vision

impairment, 4) any significant impairment in your arms that could affect tablet use, 5) diagnosis of dementia with Lewy bodies, progressive supranuclear palsy, multiple system atrophy, or vascular parkinsonism, 6) diagnosis of dementia, and 7) participation of any other therapist-supervised cognitive training.

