## **2. Statistical Analysis Plan**

Paired t-tests will be conducted to evaluate changes in outcome measures between the intervention and non-intervention periods. The outcome measures include the Montreal Cognitive Assessment (MoCA), Mini-Mental State Examination (MMSE), Digit Forward Span (DFS), Digit Backward Span (DBS), Geriatric Depression Scale (GDS), SF-36 Mental Component Summary (MCS) Score, and the Lawton-Brody Instrumental Activities of Daily Living (IADL) Scale. The null hypothesis is that the intervention results in no improvement or worse outcomes compared to the non-intervention period. The alternative hypothesis is that the intervention leads to improved outcomes. All analyses will be conducted using Python, with a one-sided significance level of 0.05.

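### SAP section 2 tests seven listed outcomes, each at an unadjusted one-sided 0.05, under one efficacy hypothesis, with no primary outcome or multiplicity rule in the text available

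*SAP*

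**What the plan says.** SAP section 2 sets out the test: "Paired t-tests will be conducted to evaluate changes in outcome measures between the intervention and non-intervention periods". It then gives the list: "The outcome measures include the Montreal Cognitive Assessment (MoCA), Mini-Mental State Examination (MMSE), Digit Forward Span (DFS), Digit Backward Span (DBS"), followed by the GDS, the SF-36 mental component summary and the "Lawton-Brody Instrumental Activities of Daily Living (IADL) Scale". That makes seven measures.

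There is one null (no improvement, or worsening) and one alternative: "The alternative hypothesis is that the intervention leads to improved outcomes". The level is set once for everything: "All analyses will be conducted using Python, with a one-sided significance level of 0.05".

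The SAP does not say how many of the seven must be significant to support the alternative. The protocol does not settle this. Its section 5 lists the assessments without ranking them. The purpose statement in the recruitment flyer begins with "if Neuro-World (mobile cognitive training games) can improve the cognitive function of adults with mild cognitive impairment (MCI"), and four of the seven tests (MoCA, MMSE, DFS, DBS) bear on that.

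**The concern.** The hypothesis concerns the intervention, but the evidence will be seven separate tests, and no rule links the two. At least three rules fit the text:

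- each outcome is reported alone, with no overall claim;
- all outcomes must improve;
- one significant outcome is enough.

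These have very different error rates. With the rule unstated, both the rule and the outcome to emphasise could be chosen after the results are known. Under the third rule, a game with no effect would yield a claim of benefit more often than the 5% attached to each test.

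**Working it through.** The available text gives no overall error rate, power or sample-size derivation, so there is no figure of the plan's to reproduce.

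**Inputs from the documents.** Seven outcomes and one-sided 0.05 per test (SAP section 2); 50 participants (protocol section 1).

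**Assumptions.** No true effect on any outcome; scores oriented so that higher is better (GDS reversed); each paired t-test holds its level; a common correlation ρ between the test statistics. The documents give no correlations, so a range is shown.

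**Any one of seven significant**

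- No assumption on correlation: at most 7 × 0.05 = 35%.
- Independent: 1 − 0.95^7 = 1 − 0.6983 = 30.2%.
- Common correlation ρ: P(any) = 1 − ∫ φ(x) · Φ((1.645 − √ρ·x)/√(1 − ρ))^7 dx.

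| ρ | 0 | 0.3 | 0.5 | 0.7 | 0.9 | 0.99 |
|---|---|---|---|---|---|---|
| P(any of 7) | 30.2% | 24.5% | 20.3% | 15.9% | 10.5% | 6.5% |

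Simulated paired t-tests at ρ = 0.5 agree: 20.6% with n = 50 and 20.5% with n = 40 or 30. The rate falls to 5% only at ρ = 1, where the seven tests are one test.

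**The four cognitive tests alone.** The same calculation with 4 in place of 7 gives 18.5%, 14.4% and 8.8% at ρ = 0, 0.5 and 0.9.

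**The other two rules**

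- All seven must be significant: at most 5%, because the joint event cannot be more likely than any single test of a true null. With no effect anywhere it is 0.07% at ρ = 0.5 and 1.6% at ρ = 0.9.
- Each outcome on its own: 5% per test, with 7 × 0.05 = 0.35 false positives expected among the seven.

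**Cost of adjusting all seven.** The first Holm step is 0.05/7 = 0.00714. Power comes from the noncentral t with n − 1 degrees of freedom and noncentrality d√n, where d is an assumed standardised paired difference. For n = 50 and d = 0.4, d√n = 2.83.

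| n | d | Power at 0.05 | Power at 0.00714 |
|---|---|---|---|
| 50 | 0.3 | 67% | 35% |
| 50 | 0.4 | 87% | 61% |
| 50 | 0.5 | 97% | 84% |
| 40 | 0.4 | 80% | 49% |

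The row with 40 completers assumes 20% loss. The documents give neither effect sizes nor loss.

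**The case against.** The strongest reply is that section 2 is a template applied to each outcome in turn. It speaks of tests and outcomes in the plural, sets a level per analysis and states no success rule. On that reading 0.05 is correct for each test. This stands: the individual tests are not at fault for want of an adjustment.

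It also follows that a reader should not infer that the plan promises a 5% overall error and breaks the promise. The SAP attaches 5% to tests and never to a combined claim. Nor can one say that the plan has a 20% or 30% error rate. Those figures hold only under the any-one rule, which the SAP does not adopt, and each depends on an assumed correlation.

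The trial may also be meant as exploratory. The protocol's title describes work towards developing a technology, and two of the three purposes in the flyer are not about efficacy. The order of purposes on a flyer is no ranking of objectives. Unadjusted tests are acceptable in exploratory work that is labelled as such. But the available text carries no such label. It states a directional efficacy hypothesis and a significance level, and that is enough to invite an overall claim.

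Finally, the part of the SAP ahead of section 1 was not available, so a rule stated there cannot be excluded. The statistical section itself was available and contains none.

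**Conclusion.** The point holds as a gap in the decision rule and is worth fixing. Seven outcomes are each tested at an unadjusted one-sided 0.05 under one hypothesis, and the available text gives no primary outcome, order or adjustment.

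If any single significant result is read as evidence of benefit, the false-claim chance exceeds 5% at every correlation below 1 in the model used. It is about 10% to 30% for common correlations of 0.9 to 0, with 35% as the upper bound. The direction does not depend on the correlation chosen, but the size does.

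All of this assumes that each paired t-test holds its level. Period and carryover effects in the crossover could disturb that and are a separate matter.

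**What to change.** **If outcome results have not been seen,** add to SAP section 2:

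> The primary outcome is [one named outcome], tested at one-sided 0.05. All other listed outcomes are exploratory and are reported as estimates with confidence intervals, without an efficacy claim.

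Alternatively, test the others by Holm's procedure at one-sided 0.05 only if the primary is significant, and claim improvement only for outcomes so rejected. With six others the first step is 0.05/6 = 0.0083. The sponsor chooses the primary. If MoCA is considered, weigh that it also decides entry: "The volunteer, scoring MoCA 17 <= (score) < 26, will be included in our study" (protocol section 2).

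**If results have been seen,** naming a primary is no longer credible. Apply Holm across all listed outcomes, or label all of them exploratory and make no overall efficacy claim.

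**Cost.** Some wording and no new data. A named primary keeps its full power, but claims on the other outcomes are restricted, and under the gated version a non-significant primary blocks them. Power for the others under gating was not computed; it depends on the primary's effect and on the correlations. Holm over all seven lowers first-step power, for example from 87% to 61% at n = 50 and an assumed standardised difference of 0.4.

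**Separately,** reconcile the daily-living scale. SAP section 2 lists Lawton-Brody, while protocol section 5 lists the Alzheimer's "Disease Cooperative Study/ADL scale adapted for MCI participants". This mismatch does not create the multiplicity, but the outcome list should be final before any adjustment is fixed.
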